This pattern, however, can be disrupted by any stressful situation, such as severe pain from surgery, which has been linked to a progressive rise in cortisol levels both intraoperatively and in the early postoperative period.

Cytokines are group of low molecular weight proteins that modulate the systemic inflammatory response elicited by surgical intervention. Increased levels of proinflammatory cytokines, including interleukin-6 (IL-6) which is the main cytokine responsible for inducing the systemic changes, is an early features of acute injury. Interleukin-6 could be a good marker for research purposes that reflects and compares postoperative stress levels.

Spine surgeries are increasingly being performed as short-stay surgical procedures, and anterior cervical decompression and fusion is one such procedure (3).Postoperative incisional pain has been described as moderate in intensity, requiring opioid analgesics in most cases. Nonetheless, opioid-related side effects such as nausea, vomiting, and respiratory depression are undesirable in these patients who are at risk for airway problems due to surgical retraction or wound hematoma(4).

Regional anesthesia inhibits the stress response to surgery and can also influence postoperative outcomes. . The endocrinal stress response to the surgical operation is reduced as a result of inhibiting afferent impulses from the surgical site. Furthermore, a reduction in this type of stress response is seen as a key indicator of a successful regional block.

Intermediate cervical plexus block (CPB) is a safe and simple technique that has been shown to provide good pain relief through blocking all four cutaneous branches of the

cervical plexus, as well as sensory and motor branches (5). Not only Intermediate (CPB) is superior to superficial CPB in terms of effectiveness, but also is safer than deep (CPB) (6).

There is a paucity of evidence for the effect of bilateral cervical plexus block for anterior cervical spine surgeries. Prior research had employed recovery questionnaire score, 24-h opioid usage and length of hospital stay in assessment of cervical plexus block effectiveness (7), however estimating the effect of Intermediate (CPB) on stress biomarkers as serum cortisol and interleukin-6 has not been discussed yet.

Aim of the work

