The aim of the present study is to investigate the effect of Bilateral Ultrasound-Guided intermediate cervical plexus Block combined with general anesthesia on the stress and inflammatory response in patients undergoing anterior cervical spine surgery (ACSS).

Objectives:

- *To compare between serum level of cortisol and interleukin-6 pre-operative and 24 hours post-operative in both groups.*
- *To identify Hemodynamics variables (mean arterial blood pressure and heart rate) peri-operatively.*
- *To assess the pain score during 1st 24 hours postoperative according to numeric pain rating scale (NPRS).*
- *To measure the incidence of complications within both groups.*

Hypothesis:

We hypothesize that intermediate cervical plexus block will offer a significant suppression of stress response and adequate post-operative analgesia in patients undergoing anterior cervical spine surgeries.

Ethical Considerations:

Our study will be conducted in Kasr El Aini Hospital, Cairo University after approval of the Research Ethics Committee. Full written informed consent will be obtained from the patients before inclusion in this study.

Methodology

Methodology

I. Study design:

A randomized controlled study.

II. Study setting and location:

The study will be conducted in the Neurosurgery operating rooms at Cairo University hospital.

III. Study population:

(66) Patients, aged from 18 to 65 years old, ASA physical status I-II, scheduled for anterior cervical spine surgery will be included in the study. Patients will be randomly allocated using concealed closed envelope method into one of two groups:

- Group A (n=33): will include the patients who will undergo bilateral ultrasound guided intermediate cervical plexus block after general anesthesia.*
- Group B (control group) (n=33): will include the patients who will undergo general anesthesia with conventional analgesia.*

IV. Eligibility Criteria

1. Inclusion criteria:

1. *ASA I & ASA II patients.*
2. *Age group: from 18 to 65 years old.*
3. *Patients undergoing anterior cervical discectomy or fixation.*
4. *Genders eligible for study: both sexes.*

2. Exclusion criteria:

- *Patient refusal.*
- *Patient Undergoing posterior fixation in addition to anterior.*
- *An allergy to local anaesthetics.*
- *Infection at block puncture site.*
- *Bleeding disorders (Coagulopathy: PTT > 40seconds, INR > 1.2, platelet count < 120 x 10³ / L.).*
- *Emergency surgeries & patients in sepsis.*

V. Study Procedures

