Once the plexus has been identified, the needle is passed through the skin, platysma, and investing layer of the deep cervical fascia, and the tip is placed adjacent to the plexus. . Following negative aspiration, 1–2 mL of normal saline is injected to confirm the proper injection site. Then after confirmation of safe needle position and absence of vascular spread, bupivacaine 0.25% (5–15 mL) is administered to envelop the plexus, and the block is repeated with the same technique on the opposite side.

(Figure 1).

[figure not shown]

Figure 1. *Cervical plexus (transverse view): desired distribution of local anesthetic (blue-shaded area) to nerve block the cervical plexus. Needle path: 1. ASM, anterior scalene muscle; CA, carotid artery; CP, cervical plexus; MSM, middle scalene muscle; SCM, sternocleidomastoid muscle.*

Group B: *Induction of general anesthesia as Group A, without performing intermediate cervical plexus block, intravenous morphine will be given in a dose of 0.1-0.2mg/kg to maintain intraoperative analgesia.*

All operations will be performed in the morning, taking into consideration circadian rhythm of hormone release. In both groups, venous blood samples to measure serum cortisol and interleukin-6 level will be collected before surgery as a baseline, then 24 hours post-operative. interleukin-6 is normally low and may be undetectable within 30-60 min after start of surgery while reaching maximum level at 24 hours post-operative.

During the intraoperative period; heart rate and mean arterial blood pressure will be recorded every 15 minutes throughout the surgery. Intravenous fentanyl bolus doses (0.5 µg/kg) will be adjusted to keep the HR and mean arterial blood pressure within 20% of the pre-induction values.

At the end of surgery, atracurium will be stopped and neuromuscular blockade will be reversed with intravenous neostigmine 0.04 mg/kg and 0.01 mg/kg atropine and endotracheal tube will be removed.

After operation, patients will be transferred to post anesthesia care unit (PACU) for complete recovery and monitoring. A standard postoperative analgesia regimen will be prescribed as intravenous paracetamol 1gm every 8 hours. Intravenous morphine 0.05 mg/kg will be given as a rescue analgesic dose if numeric analogue score was ≥ 3 . Metoclopramide 0.15 mg/kg IV will be prescribed for patients complaining of nausea or vomiting.

The maximum dose of morphine that will be given is 20 mg/24 hrs.

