The block will be considered a failed block if the patient required more than two doses of rescue analgesia in the first hour postoperatively.

Measurement tools

- *Demographic data: age, sex, body mass index (BMI).*
- *Serum cortisol and interlukien-6 pre-operative and 24 hours post-operative.*
- *Hemodynamics {heart rate, arterial blood pressure (systolic, diastolic and mean blood pressure)} will be recorded at the following intervals: baseline reading , Intraoperative 15 minutes post-intubation (pre-block), 15 minutes after the block/administration of morphine and then every 15 minutes throughout the surgery, and postoperative at 1,6,12, 24 hours..*
- *NPRS score at 15, 30, and 60 min, 6, 12, 24 hours post-operatively.*
- *Number of patients in each group who need intraoperative additional analgesic doses of fentanyl and total fentanyl dose for each patient.*
- *Total postoperative analgesic requirements.*
- *Failure rate of the block (the block will be considered a failed block if the patient required more than two doses of rescue analgesia in the first hour postoperatively).*

VI. Study outcomes

1. Primary outcomes:

- *The serum cortisol level 24 hours postoperatively.*

2. Secondary outcomes:

- *The serum interleukin-6 24 hours postoperatively.*
- *Intraoperative hemodynamics {heart rate, arterial blood pressure (systolic, diastolic and mean blood pressure)}*
- *Intraoperative additional fentanyl requirements.*
- *NPRS score postoperative during 1st 24 hours. 15, 30, and 60 min, 6, 12, and 24 hours after surgery.*
- *Time to first postoperative analgesic request (duration of analgesia).*
- *Block failure rate.*
- *Incidence of complications. (Nerve injury, Hematoma formation, LA toxicity, intravascular injection.*
- *Block failure: The block will be considered a failed block if the patient required more than two doses of rescue analgesia in the first hour postoperatively.*

Statistical Analysis

Statistical Analysis

I. Sample size

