Our primary outcome is the serum cortisol level 24 hours postoperatively. In a previous study, the serum cortisol level after 24 hours was 21.8 ± 4.7 micrograms per deciliter (mcg (ref) after lumbar fixation surgeries. We calculated a sample size that could detect a mean difference of 20% between both study groups. MedCalc Software version 14 (MedCalc Software bvba, Ostend, Belgium) was used to calculate the sample size 60 patients (30 Patient per group) at least were estimated to have a study power of 95% and an alpha error of 0.05. This number will be increased to 66 patients (33 patients per group) to compensate for possible dropouts.

Sample size calculation was performed guided by power of 95%, confidence level of 95 %.(8)

II. Statistical analysis

For data analysis, the Statistical Package for Social Science (SPSS) software, version 26 for Microsoft Windows (SPSS Inc., Chicago, IL, USA) will be used. The Chi squared test will be used to examine categorical data, which will be given as frequency (percent). The Shapiro-Wilk test will be used to verify for normality in continuous data, and the results will be provided as mean (standard deviation) or median (interquartile range) as appropriate. Depending on the data's normality, the unpaired t test or the Mann Whitney test will be used to assess it. Repeated measures will be examined using analysis of variance (ANOVA), with post-hoc pairwise comparisons using the Bonferroni tests. A P value less than 0.05 will be considered statistically significant.

References

References:

1. Arfanis K, Fioratou E and Smith A: Safety culture in anaesthesiology: Basic concepts and practical application. *Best Pract Res Clin Anaesthesiol* 25: 229-238, 2011.

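### No test is assigned by name to the primary outcome, and the baseline cortisol already being collected is not used; pre-specifying ANCOVA would settle the test and probably sharpen the estimate at almost no cost

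*Combined protocol and SAP*

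**What the plan says.** - **Primary outcome** (VI. Study outcomes): one post-treatment value, "The serum cortisol level 24 hours postoperatively".
- **Baseline** (V. Study Procedures, Study Protocol): in both groups, "venous blood samples to measure serum cortisol and interleukin-6 level will be collected before surgery as a baseline", with a second sample at 24 hours. Measurement tools lists the same pair: "Serum cortisol and interlukien-6 pre-operative and 24 hours post-operative".
- **Objective** (Objectives, first item): "To compare between serum level of cortisol and interleukin-6 pre-operative and 24 hours post-operative in both groups".
- **Analysis** (Statistical Analysis, II): methods are given by type of data, not by outcome. For continuous data, "The Shapiro-Wilk test will be used to verify for normality in continuous data", and then "Depending on the data's normality, the unpaired t test or the Mann Whitney test will be used to assess it". For repeated data, "Repeated measures will be examined using analysis of variance (ANOVA), with post-hoc pairwise comparisons using the Bonferroni tests".

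No covariate, ANCOVA or other baseline adjustment appears anywhere in the document.

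**The concern.** There are two linked gaps.

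First, the primary test is reached only by inference. A single 24-hour value falls under the t or Mann-Whitney rule. But the first objective sets pre-operative against 24-hour cortisol, so the repeated measures sentence could be read as covering cortisol too. That is an ambiguity, not a planned second test. Still, three different analyses of the primary outcome would fit the text as written.

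Second, the two-group comparison ignores a baseline measurement that the trial is already paying for. If patients with higher cortisol before surgery tend to have higher cortisol at 24 hours, adjusting for baseline removes that part of the variation from the comparison. It also corrects for chance imbalance in baseline between the groups. What is at stake is the width of the confidence interval and the power should the true difference be smaller, or the SD larger, than planned.

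**Working it through.** **Inputs.** From Statistical Analysis, I. Sample size: reference mean 21.8 and SD 4.7 mcg/dL, a 20% difference, alpha 0.05, power 95%, 30 per group, raised to 33 for dropouts. The difference is 0.20 × 21.8 = 4.36 mcg/dL. Assumptions: a two-sided test, normal data, and a baseline to 24-hour correlation ρ between 0 and 0.7, because the documents give no value.

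**The plan's own figure.** n per group = 2 × (1.960 + 1.645)² × (4.7/4.36)² = 30.2. That is 31 when rounded up, or 62 in total, against the stated 60, so the plan's figure is reproduced to within 2 patients. The sample size therefore matches an unadjusted two-sided comparison of two means.

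**Unadjusted t test.** SE = 4.7 × √(2/n), df = 2n − 2, power from the noncentral t distribution.
- n = 30: SE = 1.214, power 94.2%, 95% CI half-width 2.43.
- n = 33: SE = 1.157, power 96.0%, half-width 2.31.

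**ANCOVA.** SE = 4.7 × √(1 − ρ²) × √(2/n) × √(1 + 1/(2n − 4)), df = 2n − 3. The last factor is the expected cost of estimating the covariate slope. Example, n = 30 and ρ = 0.5: 4.7 × 0.866 × 0.2582 × 1.0089 = 1.060. The half-width is 2.0025 × 1.060 = 2.12.

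| ρ (assumed) | Power, n = 30 | Half-width, n = 30 | Change in half-width | Unadjusted n per group giving the same power | Power, n = 33 | Half-width, n = 33 |
|---|---|---|---|---|---|---|
| Unadjusted | 94.2% | 2.43 | – | 30 | 96.0% | 2.31 |
| 0 | 93.8% | 2.45 | +0.9% | 29.5 | 95.7% | 2.33 |
| 0.3 | 95.6% | 2.34 | −3.7% | 32.3 | 97.1% | 2.22 |
| 0.5 | 98.1% | 2.12 | −12.6% | 39.0 | 98.9% | 2.02 |
| 0.7 | 99.8% | 1.75 | −27.9% | 56.8 | 99.9% | 1.67 |

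Setting the two powers equal gives a break-even ρ of 0.135 at 30 per group and 0.128 at 33. At 30 per group, ANCOVA passes the stated 95% power between ρ = 0.2 (94.7%) and ρ = 0.3 (95.6%). Simulation with 40,000 trials per cell agreed with the formula to within about 0.1 point and put the ANCOVA false positive rate at 4.8% to 5.1%.

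**A smaller true effect.** For a 15% difference (0.15 × 21.8 = 3.27 mcg/dL) at 30 per group, unadjusted power is 75.5%. ANCOVA gives 74.7%, 78.6%, 85.8% and 95.7% at ρ = 0, 0.3, 0.5 and 0.7.

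**If the ANOVA sentence were applied to cortisol.** With two time points, the group-by-time test is a t test on change, with SD 4.7 × √(2(1 − ρ)) if the baseline SD is equal. At 30 per group its power is 70%, 75%, 80% and 85% at ρ = 0, 0.1, 0.2 and 0.3. It is 94.2% at ρ = 0.5, the same as the unadjusted test, and 99.5% at ρ = 0.7. Over this whole range it stays below ANCOVA.

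**The case against.** The strongest reply is that the plan is coherent as it stands. A single 24-hour value, a sample size for a difference in means and a two-group test fit together, and the test is valid. The repeated measures sentence most naturally refers to haemodynamics and pain scores, which have many time points. The gain rests on an unknown correlation. For ρ from 0 to 0.3 at 30 per group, power only moves from 94.2% to somewhere between 93.8% and 95.6%, which is unlikely to change a decision.

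Much of this stands. There is no error or bias, and the large gains need a correlation of about 0.5 or more, for which the documents offer no evidence. The introduction says of the usual cortisol pattern that "This pattern, however, can be disrupted by any stressful situation, such as severe pain from surgery". That makes a low correlation plausible, though it says nothing direct about correlation between patients.

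It does not remove the point. The 94.2% holds only for a 20% difference with a mean and SD taken from lumbar fixation, a different operation. The downside of adjusting is small and bounded, and naming the primary test is useful whatever ρ turns out to be.

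Three practical points are fair. The covariate must be drawn before allocated treatment; a baseline taken before surgery is naturally read that way, but the SAP can say so. A patient without a usable baseline would drop out of a complete-case ANCOVA, so a rule is needed. The figures above assume normal data and do not evaluate the Mann-Whitney branch.

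**Conclusion.** The concern holds as a recommended improvement in precision and specification. The generic rule covers 24-hour cortisol without being tied to it, and it leaves the baseline sample unused in the primary comparison.

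At the planning values, ANCOVA is marginally worse than the unadjusted test below a correlation of about 0.13, slightly better at 0.3, and clearly better from about 0.5, where the interval is 12.6% narrower and 30 per group does the work of 39. These results assume normal data, SD 4.7 mcg/dL, a two-sided 5% test and the stated range of correlations. The omission itself is certain; the size of the benefit is not.

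**What to change.** Before outcome data are seen, amend Statistical Analysis, II to state the following.

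1. The primary analysis is ANCOVA of 24-hour cortisol on group, with baseline cortisol as covariate, reporting the adjusted mean difference with its 95% CI.
2. The scale is fixed in advance, for example mcg/dL as in the sample size, with no change of scale or test prompted by the trial data. An unadjusted or rank-based comparison may be given as a labelled sensitivity analysis.
3. The baseline sample is drawn before allocated treatment, and there is a stated rule for a missing baseline value.
4. Repeated measures ANOVA applies to the outcomes with many time points (haemodynamics and NPRS), not to the primary test.

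Optionally, the same model can be used for log IL-6, with a rule for baseline values below the detection limit, since the protocol describes IL-6 as normally low.

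The cost is a few sentences and one degree of freedom. At the planning difference the worst case is about 0.4 points of power (0.8 points at a 15% difference), if baseline predicts nothing. No extra sample or patient is needed, and SPSS 26 fits the model.

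### Intraoperative heart rate and blood pressure series will vary in length with the operation, but the plan names only ANOVA for repeated measures and fixes no time window (low severity, cheap to improve)

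*Combined protocol and SAP*

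**What the plan says.** Under Study Procedures (Study Protocol), "heart rate and mean arterial blood pressure will be recorded every 15 minutes throughout the surgery". Measurement tools covers heart rate and systolic, diastolic and mean pressure. It lists a baseline reading, one 15 minutes after intubation (before the block), one 15 minutes after the block or morphine, "then every 15 minutes throughout the surgery, and postoperative at 1,6,12, 24 hours". The postoperative times are fixed; the intraoperative series is open-ended.

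The secondary outcomes include "Intraoperative hemodynamics {heart rate, arterial blood pressure (systolic, diastolic and mean blood pressure", with no time window. Eligibility covers "Patients undergoing anterior cervical discectomy or fixation" and sets no limit on operation length.

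Statistical Analysis, II gives repeated measures one sentence: "Repeated measures will be examined using analysis of variance (ANOVA), with post-hoc pairwise comparisons using the Bonferroni tests". It states no window, model terms, rule for operations that end early or SPSS procedure. For continuous data in general it says "the unpaired t test or the Mann Whitney test will be used to assess it", but it does not assign that sentence to the haemodynamic series.

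**The concern.** Series of unequal length are built into this design; they are not ordinary missing data. A conventional repeated-measures ANOVA needs a value in every time slot for every patient analysed. To run it, the analyst must choose a last time point, then leave out patients whose surgery ended sooner and ignore readings taken later. The plan does not fix that point, so it could be settled after the data are seen.

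At stake are the precision of one secondary comparison and the analyst's freedom over which patients and readings enter it.

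**Working it through.** **The plan's own figure.** The only stated calculation concerns the primary outcome. With SD 4.7 and a difference of 0.20 × 21.8 = 4.36 mcg/dL, n per arm = 2 × (1.960 + 1.645)² × 4.7² / 4.36² = 30.2, rounded up to 31, or 62 in total against the stated 60. Power at 30 per arm is 94.9% by the same approximation. The figure reproduces closely and has no bearing on this point. The documents give no figure for the haemodynamic analysis.

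**Inputs.** From the documents: 66 patients (33 per arm) and a 15-minute interval. Assumed, because the documents give neither operating times nor within-patient correlation:
- time from block or morphine to end of surgery is normal with mean (SD) 90 (20), 120 (30) or 150 (40) minutes, truncated below at 15;
- any two readings in a patient have correlation r = 0.3, 0.5 or 0.7;
- the group effect is constant over time.

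The last assumption matters. If the effect changes during surgery, the average to 60 minutes and the average over the whole operation are different quantities, and the percentages below do not compare like with like.

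**Method.** A patient with length L has k = floor(L/15) readings. A complete-row analysis cut at c minutes uses s = c/15 slots and keeps patients with k ≥ s. One patient's information on the average group difference is proportional to 1/(r + (1 − r)/k). Information kept is (number kept)/(r + (1 − r)/s), divided by the sum of 1/(r + (1 − r)/k) over all 66. Results are averages over 20,000 simulated trials.

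**Example: mean 120, r = 0.5, cut at 60 minutes.** Here s = 4 and 64.5 patients are kept. Information is 64.5/(0.5 + 0.5/4) = 64.5 × 1.6 = 103.2. The sum over all patients using every reading is about 115.4. The ratio is 103.2/115.4, or about 89%.

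**Results.**

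| Mean (SD), min | Cut, min | Patients kept of 66 | Information kept, r = 0.3 / 0.5 / 0.7 |
|---|---|---|---|
| 90 (20) | 60 | 61.6 | 85 / 89 / 91% |
| 90 (20) | 90 | 33.0 | 52 / 51 / 51% |
| 120 (30) | 60 | 64.5 | 82 / 89 / 94% |
| 120 (30) | 90 | 55.5 | 81 / 82 / 83% |
| 120 (30) | 120 | 33.0 | 52 / 51 / 50% |
| 150 (40) | 60 | 65.2 | 79 / 88 / 94% |
| 150 (40) | 150 | 33.0 | 51 / 51 / 50% |

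A 60-minute cut therefore keeps 62 to 65 patients and 79–94% of the information. Confidence intervals widen by a factor of 1/√0.94 = 1.03 to 1/√0.79 = 1.13. Moving the cut a little later does not always cost more. For mean 150 and r = 0.3, a 90-minute cut keeps 61.6 patients, and 61.6/(0.3 + 0.7/6) = 147.8 out of about 174.0, or 85%, against 79% at 60 minutes. The loss becomes large as the cut nears the mean operation length.

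**Detectable difference.** With a two-sample t test, two-sided 0.05, 80% power and SD held constant, 33, 32, 28 and 16.5 patients per arm can detect 0.70, 0.71, 0.76 and 1.01 SD. For mean 120, these correspond to all patients and to cuts at 60, 90 and 120 minutes.

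**Second distribution.** Lognormal lengths with mean 120 (SD 30), an assumed 6 bpm difference, SD 12 and correlation 0.6 give complete-case power of 66%, 61% and 37% at 60, 90 and 120 minutes. Using all readings gives about 69%. The pattern does not depend on the normal shape.

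**The case against.** **The plan does not name a complete-row procedure.** It says only ANOVA. An ANOVA with patient as a random factor, or an analysis of one average per patient, would fit the wording and need no complete rows. This stands: a reader might infer that the stated method is wrong or must discard patients, and the text does not support that. What remains is that no form is chosen and no window is set.

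**The large losses come from unlikely choices.** A reader might infer that about half the information is at risk. That figure arises by construction, because cutting a symmetric distribution at its mean keeps half the patients. Nothing in the documents suggests that cut would be used. This also stands; the realistic comparison is with a sensible early window, where the loss is 6–21%.

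**A fixed early window would cure the defect without a new model.** This is largely right, so the window is given below as an acceptable minimum. The mixed model adds use of readings already collected and adjustment for baseline, at little cost.

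**The t test or Mann-Whitney test could be applied at each time.** The plan does not assign them to this series, and the number of patients at each time would still fall as operations end.

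**The stakes are low.** This is one of several secondary outcomes. Fentanyl boluses "will be adjusted to keep the HR and mean arterial blood pressure within 20% of the pre-induction values", which itself narrows group differences in those two variables under any analysis. This stands and is reflected in the rating.

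**Conclusion.** The point holds as a low-severity, cheap improvement. The documents establish that the intraoperative series is open-ended, that it is a secondary outcome with no window, and that ANOVA is the only method assigned to repeated measures. The loss of patients or readings is conditional on ANOVA being run in its complete-row form.

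The size rests entirely on the assumed lengths, correlations and constant effect. With an early cut the loss is small to modest; nearer the mean operation length it grows towards half. No loss is demonstrated for this trial itself.

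Two further inferences should be resisted. Nothing shows that operation length differs between arms or that dropping short operations favours either arm, so no between-arm bias is shown. The primary outcome is a single cortisol value at 24 hours and NPRS is taken at six fixed times, so neither is touched.

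**What to change.** **Preferred.** For each of the four haemodynamic variables, replace ANOVA with a linear mixed model (SPSS MIXED, in the software already named) on all readings from 15 minutes after block or morphine to end of surgery. Include group, categorical time, group-by-time, the baseline reading as covariate and a random patient intercept. Exclude the pre-block reading from group contrasts. Prespecify group contrasts at 15, 30, 45 and 60 minutes, Bonferroni-corrected at 0.05/4 = 0.0125 each. Label the four variables supportive; the alternative is to correct across all 4 × 4 = 16 contrasts, at 0.05/16 = 0.003 each. If one average difference over surgery is wanted, take it from the same model without group-by-time and state the constant-effect assumption. That average is where the later readings add precision. Report surgery length by arm.

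**Acceptable minimum.** Keep ANOVA and prespecify an early common window, for example to 60 minutes. This removes the choice of cut-off but discards later readings.

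**Cost.** Some SAP wording and slightly more analysis work, with no new data, patients or software. The mixed model assumes that the end of surgery is unrelated to unobserved later values, given the observed readings. This matters little up to 60 minutes, where about 62 to 65 of 66 patients still contribute under the assumed lengths. Its gain over the fixed 60-minute window is the 6–21% of information shown above.

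### The repeated-measures ANOVA names neither the haemodynamic readings, the tested term nor a baseline covariate, so two pre-treatment readings may dilute a group main effect and are not used for adjustment

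*Combined protocol and SAP*

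**What the plan says.** The list of measurement tools in the combined protocol and SAP sets one haemodynamic series: "baseline reading , Intraoperative 15 minutes post-intubation (pre-block), 15 minutes after the block/administration of morphine and then every 15 minutes throughout the surgery", followed by "postoperative at 1,6,12, 24 hours". The first two readings precede the block in one arm and the morphine in the other. The second of them is labelled both intraoperative and pre-block.

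Under Study outcomes, the secondary list includes "Intraoperative hemodynamics {heart rate, arterial blood pressure (systolic, diastolic and mean blood pressure", without saying which of the intraoperative readings count.

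Statistical Analysis, section II, has one sentence for serial data: "Repeated measures will be examined using analysis of variance (ANOVA), with post-hoc pairwise comparisons using the Bonferroni tests". No readings are selected, no model term is named as the test, and no covariate is mentioned.

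**The concern.** By randomisation the expected arm difference is zero at any reading taken before the allocated treatment. If such readings enter the ANOVA as levels of time, they contribute zeros to the average arm difference, and a group main effect over the whole series is pulled toward nothing. The literal label of the pre-block reading places at least one of them inside the intraoperative outcome.

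The same two readings are also the best available predictors of a patient's later heart rate and pressure. The plan collects them and does not say that they will be used to remove between-patient variation.

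At stake is the haemodynamic comparison, which is a stated objective and a secondary outcome. A null result from an inefficient test could be read as evidence that the block has no haemodynamic effect. Because readings and term are open, the choice could also be made after the data are seen.

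**Working it through.** **The plan's own figure.** The only power calculation is for cortisol. From "the serum cortisol level after 24 hours was 21.8 ± 4.7 micrograms per deciliter" and a 20% difference, the target is 0.20 × 21.8 = 4.36, or 4.36 / 4.7 = 0.928 SD. With two-sided alpha 0.05 and 95% power, n = 2 × (1.960 + 1.645)² / 0.928² = 30.2, so 31 per group against 30 stated. That reproduces closely, but it says nothing about haemodynamics.

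**Inputs.** From the documents: 33 per arm, and 1 or 2 pre-treatment readings (pre-block only, or baseline as well). Not in the documents, and therefore assumed: an arm effect d = 0.4 SD at every post-treatment reading, equal correlation r = 0.5 between readings, and 8 post-treatment readings (surgery length is not given). All 33 per arm are taken as analysed.

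**Dilution of the main effect.** With a pre-treatment and b post-treatment readings, the average difference is d × b/(a+b).
- 1 and 8: 8/9 = 0.89, a loss of 11%
- 2 and 8: 8/10 = 0.80, a loss of 20%
- 2 and 4: 4/6 = 0.67, a loss of 33%

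**Power.** The mean of m equally correlated readings has variance V = (1 + (m−1)r)/m. The noncentrality is effect / √(2V/33), referred to the noncentral t. For the adjusted analysis, V = V_post − r²/V_pre. For group by time, λ = 33 × d² × [ab/(a+b)] / [2(1−r)], referred to the noncentral F.

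| Analysis | V or λ | Noncentrality or df | Power |
|---|---|---|---|
| Main effect, 1 pre + 8 post | V = 5/9 = 0.556 | 0.3556/0.1835 = 1.94 | 48% |
| Main effect, 2 pre + 8 post | V = 5.5/10 = 0.550 | 0.32/0.1826 = 1.75 | 41% |
| Group by time, 1 + 8 | λ = 33 × 0.16 × 0.889 = 4.69 | df 8, 512 | 27% |
| Group by time, 2 + 8 | λ = 33 × 0.16 × 1.6 = 8.45 | df 9, 576 | 47% |
| Post-treatment only, unadjusted | V = 4.5/8 = 0.5625 | 0.4/0.1846 = 2.17 | 57% |
| Post-treatment, 1 covariate | V = 0.5625 − 0.25 = 0.3125 | 0.4/0.1376 = 2.91 | 82% |
| Post-treatment, 2 covariates | V = 0.5625 − 0.25/0.75 = 0.229 | 0.4/0.1179 = 3.39 | 92% |

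**Where the gap comes from.** With one pre-treatment reading, the distance from the main effect to the adjusted test is 82 − 48 = 34 points. Dilution accounts for 57 − 48 = 9 of them and the missing covariate for 25. With two, it is 92 − 41 = 51 points, of which dilution is 16 and the covariates 35. Roughly 70% of the gap is unused baseline information.

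**Sensitivity to the correlation.**
- At r = 0.8 with 2 pre and 8 post, λ = 33 × 0.16 × 1.6 / 0.4 = 21.1. Group by time then reaches about 92%, so little is left to gain over that test.
- At r = 0.7 with the same readings, group by time has 74%.
- At r = 0.3 with 1 pre and 8 post, the main effect has 64% and the adjusted test 83%.
- With serial rather than equal correlation (0.8 between neighbours, 1 pre and 8 post), simulation gave 46% for the main effect against 66% adjusted. The gain remains but is smaller.

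**The case against.** The strongest reply is that the plan commits no error here; it is silent. The schedule is a data-collection list, not a definition of the outcome. The analysis section does not say that the pre-treatment readings are outcome levels. The pre-block label suggests that the authors regard that reading as a reference. This stands. A reader might infer that the ANOVA counts pre-block readings as outcomes, but the documents neither say so nor exclude it.

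Second, only one of the possible tests is diluted. In a group-by-time test the early readings are the reference from which the arms diverge, and that is a valid design. Comparisons of the arms at single times, if that is what the post-hoc comparisons are, are not diluted by earlier readings either. This also stands. The price of group by time is its degrees of freedom: 27% or 47% in the case worked above.

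Third, a reader might infer that most of the available power is lost. That is not supported as a general statement. Dilution alone costs 9 or 16 points in the worked case, the larger gap needs a covariate-adjusted test as yardstick, and all of it depends on a correlation the documents do not give.

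Fourth, a constant effect favours an averaged test. Intraoperative fentanyl "will be adjusted to keep the HR and mean arterial blood pressure within 20% of the pre-induction values", which may narrow arm differences, and a real effect could be brief. Averaging would then dilute it. This is a fair limit on the remedy and the reason to keep arm by time in the report.

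None of this answers the omission itself: readings, term and covariates are unspecified, and useful pre-treatment values have no stated role.

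**Conclusion.** The point holds as a specification gap with an efficiency cost. The repeated-measures sentence should name the readings, the term and the covariates. If the pre-treatment readings enter as levels of time, a main effect over all readings shrinks by 11% to 33% in the cases worked; under any of the tests, not adjusting for them is the larger loss.

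Under the stated assumptions, adjustment raises power to 82% or 92%, from 27% to 48% for the two ANOVA tests. These figures are illustrative: the effect size, the correlation and the number of readings are assumed, and at correlation 0.8 with two pre-treatment readings group by time already does nearly as well. The adjusted test was the stronger one at every equal correlation tried from 0.3 to 0.8.

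The consequence is limited. The outcome is secondary and carries no power claim, this feature does not inflate the type I error, and the primary cortisol comparison and its sample size are untouched. It should be corrected, but the trial's main conclusion does not depend on it.

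**What to change.** Add to Statistical Analysis, section II, wording to this effect: for heart rate and blood pressure, the readings after the block or morphine are the outcomes; the baseline and pre-block readings enter as covariates and not as levels of time; the test is the arm effect over the post-treatment intraoperative readings; arm by time is also reported, so that a transient difference is not missed.

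The cost is a sentence or two in the analysis section. No new data are needed and trial conduct does not change. The one downside is that a single averaged arm effect is less sensitive to a short-lived difference, which the reported arm-by-time result is there to cover.
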